## 6.3. Low Luminance BCVA

Low Luminance BCVA (LLBCVA) indicates the best possible vision that an eye can achieve with the use of trial frames/lenses following refraction and visual assessment under low luminance conditions.

If the LLBCVA assessment was done, but total letters correct is missing because neither the 4m nor the 1m assessments could be done, (i.e., only highest degree of vision was done), the total letters correct will be assigned a value of 0 and logMAR will be assigned a value of 1.7 (using the formula logMAR = 1.7 - [0.02 x total letters correct]).

Low Luminance Difference (LLD) is defined as the difference between standard photopic BCVA total letters correct and LLBCVA total letters correct.

The results for LLBCVA (letters and logMAR) and LLD (letters) at baseline and at each followup time point, and for the change from baseline, will be summarized with descriptive statistics for the treated eye and fellow eye.

LLBCVA data for individual subjects will be presented in a data listing.

### 6.4. Contrast Sensitivity

The Pelli-Robson test measures contrast sensitivity using a single large letter size with contrast varying across groups of letters. The chart uses letters (6 per line), arranged in groups whose contrast varies from high to low. Subjects read the letters, starting with the highest contrast level (log contrast level 0.00), until they are unable to read two or three letters in a single group. Each group has three letters of the same contrast level. The number of letters read correctly at each log contrast level is recorded on the eCRF. The subject is assigned a threshold score based on the log contrast of the last group in which two or three letters were correctly read. A threshold score of 2.0 indicates normal contrast sensitivity of 100 percent. Scores of less than 2.0 signify poorer contrast sensitivity. A score of less than 1.5 is consistent with visual impairment and a score of less than 1.0 represents visual disability.

Descriptive statistics will be presented for contrast sensitivity threshold scores at baseline and each scheduled follow-up time point and for the change from baseline for the treated eye and fellow eye.

Contrast sensitivity data for individual subjects will be presented in a data listing.

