11. STATISTICAL METHODS

Statistical analysis will be done by the sponsor or under the authority of the sponsor. A general description of the statistical methods to be used to analyze the efficacy and safety data is outlined below. In general, all data will be tabulated and displayed using descriptive methods only; no formal statistical testing is planned for outcome in the Safety Cohort.

Analyses will be conducted for all subjects who receive treatment in the open-label Safety Run-in phase.

After the first 21 subjects participating in the open-label safety run-in phase have completed 1 month of follow-up (the initial Safety Cohort), an analysis of data will be performed. These analyses will consist of simple descriptive statistics for key safety and efficacy measures, which will be described in the statistical analysis plan (SAP).

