11.3. Efficacy Analyses

The BCVA, LL BCVA, LLD, contrast sensitivity and growth rate of GA lesion will be summarized with descriptive statistics as specified in the SAP.

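### Contrast sensitivity: letters read are recorded at each contrast level, but SAP 6.4 summarises only a whole-group threshold, which coarsens the score and adds avoidable error to change from baseline

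*SAP*

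**What the plan says.** SAP 6.4 describes a letter chart read from high to low contrast. On structure: "Each group has three letters of the same contrast level". Reading continues "until they are unable to read two or three letters in a single group", so the test ends at the first group with none or one correct. On data capture: "The number of letters read correctly at each log contrast level is recorded on the eCRF". On scoring: "The subject is assigned a threshold score based on the log contrast of the last group in which two or three letters were correctly read". On analysis: "Descriptive statistics will be presented for contrast sensitivity threshold scores at baseline and each scheduled follow-up time point and for the change from baseline", for treated and fellow eye. No letter-level summary is planned. On individual data: "Contrast sensitivity data for individual subjects will be presented in a data listing"; the SAP does not say whether the letter counts appear in that listing.

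Protocol 11.3 brings the variable into the efficacy analysis: "contrast sensitivity and growth rate of GA lesion will be summarized with descriptive statistics", with the detail left to the SAP. Protocol 9.2.2 does not list contrast sensitivity among the primary or major secondary endpoints. Protocol 11 adds that "no formal statistical testing is planned for outcome in the Safety Cohort".

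The other two letter-chart measures are handled differently. SAP 6.1 (BCVA) and 6.3 (low luminance BCVA) both summarise total letters correct, and both tie logMAR to it by 1.7 - 0.02 x letters, so every letter counts.

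**The concern.** The letter-level information is already collected, and the rule leaves most of it out of the summary. Two of three and three of three in the last passed group score the same. So do none and one in the failed group, and misses in earlier passed groups have no effect. Conversely, one misread letter at the pass mark moves the score by a whole group.

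What is at stake is precision, not bias: mean change is unaffected by the choice of score. In a descriptive analysis of about 21 subjects, the means, SDs and individual changes are the whole result for this variable. Avoidable scoring noise widens the reported spread and makes a small individual gain or loss harder to see. No reason is given for treating this chart differently from the two acuity charts.

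**Working it through.** **Nothing to reproduce.** Neither document states an SD, repeatability, group step or slope for contrast sensitivity. All results below are in units of one group step, so the variance ratios do not depend on the chart's step size.

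**Step 1: what the two scores do.** Taken from SAP 6.4: three letters per group, the first group at log contrast 0.00, a stop at the first group with fewer than two correct, and a threshold at the last group with two or three correct. By-letter score, in group steps: total letters correct / 3 - 1, counting letters up to and including the failed group. If k groups are read in full and none in the next, this is 3k/3 - 1 = k - 1, the same as the threshold.

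| Letters correct by group | Threshold (steps) | Letters | By-letter (steps) |
|---|---|---|---|
| 3, 3, 3, 3, 1 | 3 | 13 | 13/3 - 1 = 3.33 |
| 3, 3, 3, 2, 0 | 3 | 11 | 11/3 - 1 = 2.67 |
| 3, 3, 3, 1 | 2 | 10 | 10/3 - 1 = 2.33 |

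Rows 1 and 2 differ by two letters and tie on the threshold. Rows 2 and 3 differ by one letter and are a full step apart on the threshold, against one third of a step by letter.

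**Step 2: size of the error component.** Simulation of 100,000 eyes per setting, tested twice with no true change, under the SAP stopping rule. Assumed, because the documents are silent: logistic letter recognition with scale 0.1-1.0 step, guessing 0-10%, lapses (a visible letter misread) 0-5%, and visit-to-visit SD of the eye's own threshold (drift) 0-1 step. The result is the variance of change by group divided by that by letter:

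| Setting | Ratio |
|---|---|
| No lapses, no drift, no guessing | 1.57-1.90 |
| No lapses, no drift, 4% guessing | 1.54-1.74 |
| No lapses, no drift, 10% guessing | 1.45-1.67 |
| 1% lapses, no drift | 1.08-1.52 |
| 2% lapses, no drift | 1.05-1.46 |
| 5% lapses, no drift | 1.13-1.37 |
| Drift SD 0.25 step, no lapses | 1.31-1.54 |
| Drift SD 0.5 step, no lapses | 1.13-1.41 |
| Drift SD 1 step, no lapses | 1.04-1.22 |

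The ratio exceeds 1 in every setting. The overall span is 1.04 to 1.90, an inflation of 4% to 90%.

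**Step 3: why drift and true change dilute it.** Both add about the same variance to either score. If the ratio from letter sampling alone is R0 and the added variance is D times the by-letter error variance, then R = (R0 + D)/(1 + D), approximately. The fall in SD from by-letter scoring is 1 - 1/sqrt(R). Take R0 = 1.70 (scale 0.5 step, no guessing, lapses or drift):

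- D = 0: R = 1.70, SD lower by 1 - 1/1.304 = 23%.
- D = 1: R = 2.70/2 = 1.35, SD lower by 1 - 1/1.162 = 14%.
- D = 5: R = 6.70/6 = 1.12, SD lower by 1 - 1/1.057 = 5%.

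**Step 4: the reported quantity.** SAP 6.4 reports the SD of observed change, which includes true differences between subjects. With no lapses and no drift (scale 0.2-1.0 step, guessing 0-10%), by-letter scoring lowers that SD by:

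- 20-27% if the SD of true change is 0,
- 12-18% at half a step,
- 5-13% at one step,
- 2-7% at two steps.

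At one step, also allowing lapses of 0-2% and drift of up to one step, the range is about 2-13%.

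**The case against.** The SAP rule is complete and reproducible, no passage contradicts it, and the interpretation bands at 1.0, 1.5 and 2.0 are defined on that threshold score. No test, confidence interval, responder cut-off or sample size depends on contrast sensitivity, and it is not a listed endpoint. Choosing a finer score is a choice between two workable methods. All of this stands, and it is why the point is low in severity and the threshold score should stay.

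Three stronger readings are tempting, and the documents support none of them:

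- A reader might infer that group scoring inflates error variance by more than half as a matter of course. That holds mainly with almost no lapses and no drift, and the documents do not show that this case applies. With drift of half a step alone, the whole range lies below 1.5.
- A reader might infer that data are discarded. The counts stay on the eCRF, and individual contrast sensitivity data are to be listed. The counts are left out of the summary score only.
- A reader might convert the gain into an equivalent larger sample. The 21 subjects were chosen for safety and usability of the Delivery System (Protocol 11.2), and no inference on contrast sensitivity is planned, so such a figure has nothing to refer to.

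The by-letter score also has gaps of its own. Neither document gives the group step. Near the floor the two scores part: an eye reading two letters in the first group and none after has threshold 0.00 but a by-letter value of 2/3 - 1 = -1/3 step. This can matter, since enrolled study eyes have foveal atrophy and BCVA of 20/80 to 20/800 (Protocol 4.1). The threshold rule is not free of the problem either: an eye with none or one correct in the first group has no qualifying group, and SAP 6.4 does not say what score it gets.

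**Conclusion.** The point holds as a precision improvement. Whole-group scoring of letter counts that are already collected gives a coarser score and a noisier change from baseline; the direction was the same in every setting tried. The inflation of measurement-error variance is roughly 4% to 90%, and the reduction in the SD of observed change is about 2-13% if true change has an SD of one group step. Both ranges rest on assumed slopes, guessing, lapses and drift, and neither can be narrowed from the documents. The practical consequence is modest: one descriptive summary, with no decision attached. Low severity, worth doing because it costs almost nothing.

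**What to change.** In SAP 6.4:

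- Add a by-letter score: group step x (total letters correct / 3 - 1), counting letters up to and including the group at which reading stopped.
- State the chart's group step in log units.
- State how eyes reading fewer than three letters are scored, and what threshold score applies when the first group is failed.
- Summarise the by-letter score and its change from baseline, for treated and fellow eye at each scheduled visit, alongside the threshold score. Keep the threshold score for the 1.0, 1.5 and 2.0 bands and say that the bands refer to it alone.
- Say that the data listing shows the letter counts.

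The cost is one derived variable from data already on the eCRF and extra rows in an existing table, with no new assessment or visit. The small downside is that two scores must be presented and told apart.

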### 7. PHARMACOKINETICS/PHARMACODYNAMICS

Not applicable.

### 8. IMMUNOGENICITY

Immunogenicity data including the sample ADA (anti-drug antibodies) status and mean result FACS (fluorescence activated cell sorting) screen for individual subjects will be presented in a data listing.

### 9. HEALTH ECONOMICS AND HEALTH OUTCOMES

Not applicable. Since PROs and questionnaire results (NEI-VFQ-25, SF-36, and Near Vision Subscale, FRI, PGIC-S, PGIC-Q, CGIC) are not included as study objectives as of Protocol Amendment 3, these data will not be summarized in tables or listings for the CSR.

Palucorcel (CNTO 2476)

## ATTACHMENTS

#### 1. DATA HANDLING RULES FOR MISSING OR PARTIAL DATES

#### **Onset/Start Date**

If only the day part of the event onset/start date is missing and occurs in the same month and year as the Surgery Date, then the Surgery Date will be used as the onset/start date of the event.

Otherwise, if only the day part of the event onset date is missing, the first day of the month will be used to complete the onset/start date of the event.

If only the day and the month parts of the event onset/start date are missing and the event occurs in the same year as the Surgery Date, then the Surgery Date will be used as the onset/start date of the event. Otherwise, if only the day and the month parts of the event onset/start date are missing, January 1st will be used to complete the onset/start date of the event.

If the event onset/start date is equal to the Surgery Date, but the clock time is missing, then the event will be considered treatment emergent; i.e., as if onset/start time was during or after surgery.

If the time of onset of an event is missing, no imputation will be made.

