12.1. Definitions

12.1.1. Adverse Event Definitions and Classifications

Adverse Event

An AE is any untoward medical occurrence in a clinical study subject administered a medicinal (investigational or non-investigational) product. An AE does not necessarily have a causal relationship with the treatment. An AE can therefore be any unfavorable and unintended sign (including an abnormal finding), symptom, or disease temporally associated with the use of a medicinal (investigational or non-investigational) product, whether or not related to that medicinal (investigational or non-investigational) product (definition per the International Conference on Harmonisation [ICH]).

This includes any occurrence that is new in onset or aggravated in severity or frequency from the baseline condition, or abnormal results of diagnostic procedures, including laboratory test abnormalities.

Note: The sponsor collects AEs starting with the signing of the ICF (refer to Section 12.3.1, All Adverse Events, for time of last AE recording).

Serious Adverse Event

An SAE based on ICH and EU Guidelines on Pharmacovigilance for Medicinal Products for Human Use is any untoward medical occurrence that at any dose:

- Results in death
- Is life-threatening
(The subject was at risk of death at the time of the event. It does not refer to an event that hypothetically might have caused death if it were more severe.)
- Requires inpatient hospitalization or prolongation of existing hospitalization
- Results in persistent or significant disability/incapacity
- Is a congenital anomaly/birth defect
- Is a suspected transmission of any infectious agent via a medicinal product
- Is Medically Important*

*Medical and scientific judgment should be exercised in deciding whether expedited reporting is also appropriate in other situations, such as important medical events that may not be immediately life threatening or result in death or hospitalization but may jeopardize the subject or may require intervention to prevent 1 of the other outcomes listed in the definition above. These should usually be considered serious.

If a serious and unexpected AE occurs for which there is evidence suggesting a causal relationship between CNTO 2476, the delivery system, or the device and the event, the event must be reported as a serious and unexpected suspected adverse reaction even if it is a component of the study endpoint.

Unlisted (Unexpected) Adverse Event/Reference Safety Information

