## 5. SAFETY

The verbatim terms used in the eCRF by investigators to identify adverse events (AEs) will be coded using the Medical Dictionary for Regulatory Activities (MedDRA). All reported AEs with onset from the surgery start date and onwards (i.e., treatment-emergent (TE) AEs, and AEs that have worsened since baseline) will be included in the analysis. Note that after Month 12, only serious AEs and ocular AEs are collected as per protocol. Missing or incomplete AE onset dates will be handled as described in Attachment 1.

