### 5.1. Ocular AEs

Ocular TE AEs include those with system organ class (SOC) = "Eye Disorders" or those with eye specified on the eCRF. The number and percentage of subjects who experienced at least 1 ocular TE AE will be presented in summary tables by preferred term according to MedDRA terminology as well as by affected eyes (events occurring in the treated eye only, in the fellow eye only, and in both eyes).

Serious ocular TE AEs will be summarized similarly.

Ocular TE AEs will be summarized by severity, and by relationship indicated on the eCRF (study treatment, device, and surgical procedure).

Ocular TE AEs will also be summarized by timing: for those with onset on or before the Week 4 visit date, and those with onset after the Week 4 visit date.

Individual subject ocular AEs will be presented in a data listing.

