#### **Stop Date**

If only the day part of the event stop date is missing, the last day of the month will be used to complete the stop date of the event.

If only the day and the month parts of the event stop date are missing, December 31st will be used.

If the stop date is completely missing and the ongoing status is also missing, the event will be considered as ongoing.

Any medication which is ongoing will be considered concomitant.

The imputed onset and stop dates will be verified to ensure that the onset date is prior or equal to the stop date.

The imputed dates will be used to determine the treatment-emergent status of the AE or the concomitant/prior status of medications, and to calculate study day and/or duration as needed.

medications, and to calculate study day and/or duration as needed.

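### The partial-date rule biases the Week 4 timing split of ocular AEs toward early onset, and it gives no outcome when an imputed onset falls after the stop date

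*SAP*

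**What the plan says.** SAP section 5 defines the AEs to be analysed as "All reported AEs with onset from the surgery start date and onwards" and adds: "Missing or incomplete AE onset dates will be handled as described in Attachment 1".

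Attachment 1 (Onset/Start Date) has these rules:

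- **Day missing, surgery month.** The rule opens "If only the day part of the event onset/start date is missing and occurs in the same month and year as the Surgery Date" and assigns the Surgery Date.
- **Day missing, any other month.** The first of that month is used.
- **Day and month missing, surgery year.** If "the event occurs in the same year as the Surgery Date, then the Surgery Date will be used as the onset/start date".
- **Day and month missing, any other year.** 1 January is used.
- **Time missing on the day of surgery.** "If the event onset/start date is equal to the Surgery Date, but the clock time is missing, then the event will be considered treatment emergent".

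None of these rules refers to the stop date. Partial stop dates go to the last day of the month or to 31 December. Attachment 1 (Stop Date) then says: "The imputed onset and stop dates will be verified to ensure that the onset date is prior or equal to the stop date". It does not say what follows if the check fails.

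SAP section 5.1 states: "Ocular TE AEs will also be summarized by timing: for those with onset on or before the Week 4 visit date", set against those with onset after that visit. On when AE collection begins, Protocol 12.1.1 states: "The sponsor collects AEs starting with the signing of the ICF". Protocol 9.1.1.1 allows up to 45 days of screening before treatment.

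**The concern.** One imputed date serves two purposes. For treatment-emergent status, moving an uncertain onset to the Surgery Date is the usual cautious choice, because the event is counted. For the Week 4 split it is not neutral. Incomplete post-operative onsets are placed at or near the earliest date they could have, so errors run only from late to early.

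The split separates events close to the procedure from those arising in follow-up. Safety of the surgical approach and Delivery System is the primary objective, there is no control group, and Protocol 3.2 gives long-term safety follow-up as the purpose of the amended design. Understating late ocular AEs works against that purpose.

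The second issue concerns AEs that arise between consent and surgery. With a partial onset in the surgery month or year, the rule gives them a post-operative onset date even when the recorded stop shows that they ended before surgery. The plan leaves the programmer to decide how to classify such a record.

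**Working it through.** The documents give no figure on this point, so there is none to reproduce. The rules were applied literally to all 366 surgery dates of 2016, with true onsets 0 to 365 days after surgery. The Week 4 visit was taken as surgery + 28 days, with + 25 and + 31 as a range (Protocol Table 1 gives ±3 days; Protocol 9.1.1 says ±3 business days).

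**1. Year-only onset in the surgery year.** All 56,953 combinations with a true onset after Week 4 in the surgery year are imputed to Day 1 and counted as early. Example: surgery 10 February, true onset 20 November (284 days later), imputed onset 10 February.

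To illustrate size, assume surgery on the 15th and true onset uniform from surgery to 31 December. Let L be the days left in the year, counting the day of surgery. The first 29 days (day 0 to day 28) are truly early, so the misplacement probability is (L − 29)/L, or zero if L is 29 or less.

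| Surgery | L | Misplaced |
|---|---|---|
| 15 January | 352 | 323/352 = 0.92 |
| 15 June | 200 | 171/200 = 0.855 |
| 15 September | 108 | 79/108 = 0.73 |
| 15 October | 78 | 49/78 = 0.63 |
| 15 November | 47 | 18/47 = 0.38 |
| 15 December | 17 | 0 |

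These are upper-end values. In general the probability is 1 minus the share of such onsets that truly fall by Week 4. If that share were 0.5 the probability would be 0.5, and if it were 0.9 it would be 0.1.

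The December zero covers onsets in the surgery year only. A year-only onset in the following year goes to 1 January, which is before the 12 January visit and so also early.

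**2. Day-missing onset in the month of the Week 4 visit, when that is later than the surgery month.** The first of the month is never after the visit, so all such AEs are placed early. Example: surgery 15 June, visit 13 July, onset recorded as July, imputed 1 July. True onsets on 14–31 July are wrong: 18/31 = 58%. Over the 336 surgery dates of 2016 whose visit falls in a later month, the average under uniform onset is 5,376/10,248 = 52%, ranging from 3% to 97% with the day of the visit.

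**3. Day-missing onset in the surgery month.** True onset is at most 30 days after surgery. With the visit at + 28, misplacement needs surgery on day 1 or 2 of the month (25 date combinations in the year). At + 25 it needs day 1 to 5 (151 combinations). At + 31 it cannot occur.

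**4. Treatment-emergent status, surgery 20 May.**

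| Recorded onset | Recorded stop | Imputed onset | Stop used | Order check |
|---|---|---|---|---|
| May | 10 May | 20 May | 10 May | fails |
| Year only | 28 April | 20 May | 28 April | fails |
| Year only | April | 20 May | 30 April | fails |
| May | May | 20 May | 31 May | passes |
| Year only | Year only | 20 May | 31 December | passes |

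The first three AEs ended before surgery. The check flags them and the plan gives no next step. The last two could have ended before or after surgery, and the rule counts them as treatment-emergent. The first-of-month and 1 January rules assign the earliest possible date, so they cannot create an onset after a valid stop. Only the Surgery Date rule can.

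**The case against.** **The link to the timing table is inferred.** Attachment 1 lists the uses of imputed dates as treatment-emergent status, prior or concomitant status, study day and duration. It does not name the Week 4 split. That is fair, but section 5 applies Attachment 1 to incomplete AE onsets in general, and section 5.1 supplies no alternative.

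**Few dates will be affected.** Visits are frequent in the first three months, AE collection is continuous and queries can be raised, so a year-only onset for a post-operative ocular AE should be rare. This stands, and it limits the size of the problem.

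**The uniform assumption is unfavourable.** The synopsis and Protocol 3.1 expect most procedure-related AEs to be apparent within hours of surgery. Where onsets cluster early, the imputation is usually right. This also stands. A reader might take 0.92 as the expected error, but the documents give no basis for that.

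**Consequences are contained.** No AE is lost. The overall, serious, severity and relationship summaries do not use the split, nor do the events of special interest, and ocular AEs are listed individually. The analysis is descriptive.

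Two stronger readings are tempting and should be resisted. One is that incomplete onsets in the surgery month are also pushed across Week 4. They almost never are, because that month ends at or near the visit. The other is that AEs known to have ended before surgery will be counted as treatment-emergent in the safety tables. The order check stops such records, so what is missing is a stop-date condition and a stated action.

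**Conclusion.** The point holds as a limited, one-directional bias in one descriptive table, plus a gap in the date rules. Followed as written, the SAP counts every year-only onset that truly fell after Week 4 in the surgery year as early. It does the same for every day-missing onset in a Week 4 visit month that follows the surgery month, and about half of these would be wrong under uniform onset. Day-missing onsets in the surgery month are almost unaffected.

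The range of 0.38 to 0.92 for mid-month surgery from January to November, and zero for mid-December, is conditional on a year-only onset in the surgery year and on uniform onset. It falls if onsets cluster soon after surgery. With 21 subjects, one misplaced subject is 1/21 = 4.8 points. The documents do not say how many dates will be partial; that the number is small is an assumption.

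For treatment-emergent status the rule is cautious, and it should stay so where the stop date leaves doubt. The defect there is that a stop date known to precede surgery is ignored and the failed order check has no defined outcome.

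**What to change.** 1. **Attachment 1.** Impute onset to the Surgery Date only when the stop date, complete or imputed to its latest possible date, is missing or not before the Surgery Date. State that an AE whose latest possible stop is before surgery is not treatment-emergent. This also settles the order-check failures that the imputation creates. AEs whose partial stop could fall on or after surgery stay treatment-emergent as the cautious choice.
2. **Section 5.1 timing table.** Place an ocular AE as early or late only if its earliest and latest possible onset fall on the same side of the Week 4 visit date; a recorded stop date can narrow that range. Show all others in a row labelled *onset date incomplete*.

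The cost is a few sentences of SAP text, one extra table row and slightly more programming. No new data are needed.
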